3.2 RESPONSIBILITY FOR ANALYSES/IN-HOUSE BLINDING

The statistical analysis of the data obtained from this study will be the responsibility of the designee of the Sponsor.

This study will be conducted as a double-blind study under in-house blinding procedures. The official, final database will not be unblinded until medical/scientific review has been performed, protocol deviations have been identified, and data have been declared final and complete. The investigator site personnel and the participants will be blinded to intervention assignment until the entire study is completed.

The Clinical Biostatistics department will generate the randomized allocation schedule(s) for study intervention assignment. Treatment assignment will be implemented in an IRT system by a study vendor according to the adaptive allocation scheme provided in Section 6.3.1 – Intervention Assignment of the protocol.

Unblinding for Interim Efficacy and Safety Analyses

Planned interim analyses are described in Section 3.7 – Interim Analyses. Study enrollment is likely to be ongoing at the time of any interim analyses. Blinding to treatment assignment will be maintained at all investigational sites. The results of interim analyses will not be shared with the investigators prior to the completion of the study.

Treatment-level results of the interim efficacy and safety analyses will be provided by the external unblinded statistician to the DMC. Limited additional Sponsor personnel may be unblinded to the treatment-level results of the interim analyses, if required, in order to act on the recommendations of the DMC. The extent to which individuals are unblinded with respect to results of interim analyses will be documented by the external unblinded statistician.

The DMC will serve as the primary reviewer of the results of the interim efficacy and safety analyses and will make recommendations for discontinuation of the study or modification to an Executive Oversight Committee (EOC) of the Sponsor. If the DMC recommends modifications to the design of the protocol or discontinuation of the study, the EOC may be unblinded to the results at the treatment-level in order to act on these recommendations. Additional logistical details will be provided in the DMC Charter.

Prior to final study unblinding, the external unblinded statistician will not be involved in any discussions regarding modifications to the protocol, statistical methods, identification of protocol deviations, or data validation efforts after the interim analyses.

3.3 HYPOTHESES/ESTIMATION

The primary and secondary hypotheses for this study are stated in Section 3 – Objectives/Hypotheses and Endpoints of the protocol.

3.4 ANALYSIS ENDPOINTS

Efficacy and safety endpoints for evaluation are listed below.

3.4.1 Efficacy Endpoints

3.4.1.1 Primary Efficacy Endpoint

- LCQ total score measured as change from baseline at Week 12

3.4.1.2 Secondary Efficacy Endpoint

- Cough Severity VAS score measured as change from baseline at Week 12

3.4.1.3 Exploratory Efficacy Endpoints

- CSD total score measured as change from baseline at Week 12
- PGIC measured at Week 12
- WPAI measured as change from baseline at Week 12

3.4.2 Safety Endpoints

- Adverse events
- Study intervention discontinuations due to an adverse event

3.4.3 Derivations of Efficacy Endpoints

Baseline for efficacy variables is defined as the last non-missing value prior to the first study treatment.

Data Handling Rules for Efficacy Endpoints

- **LCQ Total Score**

There are three domains in the LCQ instrument: Physical (items 1, 2, 3, 9, 10, 11, 14 and 15), Psychological (items 4, 5, 6, 12, 13, 16, and 17), and Social (items 7, 8, 18, and 19). For each domain, the domain score (range 1-7) is the sum of individual item score within the domain divided by the number of items in the domain. The LCQ total score (range 3-21) is the sum of the three domain scores.

The Physical domain score will be considered as missing if more than 2 items are missing. If there is only 1 missing item, the Physical domain score will be based on the actual non-missing items. Psychological domain score will be derived in a similar fashion. Social domain score will be considered as missing if any item is missing. The LCQ total score will be considered as missing if any of the 3 domain scores is missing.

- **Cough Severity VAS score**

Cough severity VAS is scored from 0 to 100 using a 100 mm visual analogue scale. Mean weekly VAS score will be derived as the average of the VAS scores collected during the week prior to each visit. Baseline is defined as the average of VAS scores collected during the week prior to Day 1 (Day -7 to Day -1).

The mean weekly VAS score will be considered as missing if there are more than 3 missing days during the week prior to each visit. If there are less than 7 but at least 4 non-missing days during the week prior to a visit, the mean weekly score will be based on the actual non-missing days of the week prior to the visit.

- **CSD Total Score**

The daily CSD instrument has a total of 7 items, each with scores ranging from 0 (best) to 10 (worst). The total daily CSD score is the sum of these seven item scores. Mean total daily score (the sum of 7 item scores divided by 7) and three subscales (cough frequency, intensity, and disruption) will be derived for each day. Mean weekly total score is defined as the average of the mean total daily scores collected during the week prior to each visit. Mean weekly subscales will be derived in a similar fashion. Baseline is defined as the average CSD scores collected during the week prior to Day 1 (Day -7 to Day -1).

[figure not shown]
The mean weekly total score will be considered as missing if there are more than 3 missing days during the week prior to each visit. If there are less than 7 but at least 4 non-missing days during the week prior to a visit, the mean weekly total score will be based on the actual non-missing days of the week prior to the visit. Mean weekly subscales will be derived in a similar fashion.

3.5 ANALYSIS POPULATIONS

3.5.1 Efficacy Analysis Populations

The FAS population will serve as the primary population for the analysis of efficacy data in this study. The FAS population consists of all randomized participants who have taken at least 1 dose of study intervention. For endpoints that are measures of change from baseline, participants need to have baseline and at least one post-baseline measurement for inclusion in the analysis of each specific endpoint. Per-Protocol (PP) population excludes participants due to important violations from the protocol that may substantially affect the results of the primary efficacy endpoint. Potential violations that may result in the exclusion of a participant from the PP population will be specified in this document approaching database lock. The final determination on important protocol violations, and thereby the composition of the PP population, will be made prior to the first unblinding of the database and will be documented in a separate memo. A supportive analysis using the PP population may be performed for the primary efficacy endpoint if the proportion of the participants with important protocol deviations is >10%.

The list below shows important protocol violation criteria that may be considered as affecting the results of the efficacy endpoints:

Participants will be included in the intervention group to which they are randomized for the analysis of efficacy data using the FAS population. Details on the approach to handling missing data are provided in Section 3.6 – Statistical Methods.

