9.5 Analysis Populations

9.5.1 Efficacy Analysis Populations

The FAS population will serve as the primary population for the analysis of efficacy data in this study. The FAS population consists of all randomized participants who have taken at least 1 dose of study intervention.

Participants will be included in the intervention group to which they are randomized for the analysis of efficacy data using the FAS population. Details on the approach to handling missing data are provided in Section 9.6.

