3.6.1 Statistical Methods for Efficacy Analyses

The analysis of efficacy endpoints will be based on the FAS population. Unless otherwise specified, analyses will include all follow-up efficacy data collected for those participants who discontinued treatment.

Primary Efficacy Analysis

The LCQ is collected at baseline and after administration of the study intervention at Weeks 6 and 12. The primary efficacy endpoint of this study is the LCQ change from baseline in total score. The primary analysis approach will be conducted utilizing the longitudinal ANCOVA model. In this model, the response vector consists of the LCQ change from baseline in total score at each post-Baseline visit. The model will include factors for intervention group, visit, interaction of treatment by visit, gender, and the baseline LCQ score. The model will use all available LCQ change from baseline in total score at Weeks 6 and 12. Contrasts will be constructed to compare the Gefapixant intervention group to the Placebo group at Week 6 and Week 12. The least squares mean change from baseline with the associated standard errors will be displayed for each intervention group. Overall estimated treatment differences (Gefapixant – Placebo) along with corresponding p-values and 95% CIs will also be presented, with the exception of the primary efficacy endpoint, in which the CI width will be adjusted for an IA.

Secondary Efficacy Analysis

The secondary efficacy endpoint will be analyzed using a similar longitudinal ANCOVA model as used for the primary efficacy analysis. The model will include terms for intervention group, visit, interaction of treatment by visit, gender, and baseline score.

[Table 1](#) summarizes the analysis strategy of the primary and secondary efficacy endpoints.

Table 1 Analysis Strategy for Key Efficacy Endpoints

Endpoint/Variable (at Week 12)	Statistical Method	Missing Data Approach
Primary		
Change from baseline in LCQ total score	Longitudinal ANCOVA	Model-based ^a
Secondary		
Change from baseline in Cough Severity VAS score	Longitudinal ANCOVA	Model-based ^a
ANCOVA = analysis of covariance; LCQ = Leicester Cough Questionnaire; VAS = Visual Analogue Scale		
^a Includes data collected after early intervention discontinuation.		

Exploratory Efficacy Analysis

- **CSD Total Score**

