A participant will be considered for inclusion in the assessment of an efficacy endpoint if the CSD and Cough Severity VAS are completed on at least 4 days during the 7-day period prior to a post-Baseline visit (other ePROs are completed at the clinic visit only). All efficacy analyses will be conducted based on the observed data only. No imputation is planned for the missing diaries or missing questionnaire items. The pattern of missing is assumed to be missing at random (MAR). The missing pattern will be inspected to determine if the MAR assumption is met. Sensitivity analyses will be implemented to explore the impact of departures from the assumption made in missing diaries.

The longitudinal ANCOVA model (aka. LDA method) assumes that data are missing at random. In this study, it is expected that missing at random and missing completely at random (MAR/MCAR) mechanisms will underlie most of the missingness, and the proportion of data missing not at random (MNAR), driven solely by unobserved values of the study endpoints, will be small.

In addition to the analysis approach specified in the above mentioned primary efficacy endpoint analysis section, the following sensitivity analyses will be used to assess the robustness of the primary analysis approach.

Tipping-point Multiple-imputation Analysis

The Variant 3 of the tipping point as described in paper [Ratitch et al. 2013] will be used. In that approach, missing data are first imputed for all visits under the MAR assumption, and then the worsening/shift is applied. This is repeated with increasing the delta-shift (worsening) until the result is no longer statistically significant. Specifically, for a given constant, c , the tipping point analysis is conducted in a fashion similar to that used in standard multiple imputation, whereby m ($=100$) complete datasets are randomly generated using the original observed dataset. These m complete datasets are subsequently analyzed using the primary model, and the results of those analyses are then combined. The construction and analysis of these m ($=100$) datasets requires four primary steps:

- 1) Using a Markov Chain Monte Carlo method, make the observed dataset monotone-missing. This will be accomplished for each treatment group using “proc mi” within SAS 9.3 or higher by utilizing the options “mcmc chain=multiple impute=monotone;”, in conjunction with all of the covariates (excluding treatment)

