included in the primary analysis model. The random seed will be set equal to 72644243. This step will generate m monotone-missing datasets.

- 2) Applying parametric regression to the monotone-missing datasets, impute all the missing values. This will be accomplished for each treatment group using “proc mi” within SAS 9.3 or higher utilizing the option “monotone reg”, in conjunction with all of the covariates (excluding treatment) included in the primary analysis model. The random seed will be set equal to 72644243. This step will generate m complete datasets.
- 3) To implement the tipping-point aspect of the procedure, subtract a constant c from each of the imputed values of the active arms (to the detriment of active).
- 4) Analyze each of the post-imputation complete datasets using the primary model, obtaining point estimates for the mean of interest (e.g. change-from-baseline treatment difference at 12 weeks) and the associated variance.

Using “proc mianalyze” within SAS 9.3 or higher, the $m=100$ means and variances from the m analyses will be combined to obtain the final test statistic and p-value (Rubin, 1987). The final test statistic $\bar{Q} / (T^{-1/2})$ is approximately distributed as t_v , where \bar{Q} is the sample mean of the m treatment difference estimates, $T = \bar{U} + (m+1) (B/m)$, \bar{U} is the sample mean of the m variance estimates, and B is the sample variance of the m treatment difference estimates. The degrees of freedom, v , will be computed as follows [Barnard and Rubin, 1999]: $v = [(v_1)^{-1} + (v_2)^{-1}]^{-1}$, where $v_1 = (m-1) [1 + (\bar{U}/(1+m^{-1}) B)]^2$ and $v_2 = (1-\gamma) v_0 (v_0 + 1) / (v_0 + 3)$, with $\gamma = (1+m^{-1}) B / T$ and where v_0 represents the complete-data degrees of freedom .

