This procedure will be repeated (using the same m imputed datasets) until the smallest c is found such that the significant result turns non-significant (i.e., $p > 0.05$). This tipping point value c provides a measure of robustness of the primary result. A relatively large value of c implies better robustness of the primary analysis against the impact of missing data in the study. It is noted that when $c=0$ the tipping point analysis described above corresponds to an analysis conducted under the assumption that the missing data are MAR. For values of c larger than 0, the tipping point analyses do not assume that the missing values follow a MAR mechanism. In fact, the analysis is based on a special MNAR mechanism in which all missing data across the arms are assumed to have a worse response by a constant amount of c than the values would have had under MAR.

Jump-to-reference (J2R) Multiple-imputation Analysis

J2R imputation falls under the category of pattern mixture models known as reference-based imputation (RBI). The RBI approach uses different imputation models for missing data in different treatment groups. In J2R, missing data in the control group are imputed under the MAR assumption, while missing data in the treatment groups are imputed under a MNAR assumption using the control group profile for time points after withdrawal.

The following steps will be used to implement the J2R multiple-imputation analysis.

- 1) A parameter-estimation model is fitted using PROC MCMC. All the covariates included in the primary analysis will be used for the parameter-estimation model. For the MCMC procedure, an initial random seed=72644243 will be used. N=500 sets of pseudo-independent samples of the model parameters will be drawn from the joint posterior distribution.

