- 2) The imputation model is built, where, for each pattern of withdrawal, a predicted value model is created using the parameters estimated in Step 1. The random seed for the imputations is 72644243. For subjects in the control (reference) group, the predicted means are calculated under MAR assumption; for subjects in the other treatment arms, the predicted means are calculated under MNAR using the jump-to-reference approach, that is, the mean profile is based on the same treatment arm before withdrawal and ‘jumps’ to the mean profile based on the reference arm after withdrawal. A complete dataset will be generated using the imputation model for each set of the N=500 parameters obtained in Step 1.
- 3) For each of the imputed complete datasets, an ANCOVA model will be used for the change from baseline values at last time point. The model will include the same covariates as in the primary analysis model. The treatment difference across the 500 datasets will then be combined using PROC MIANALYZE, i.e., using Rubin’s rule for multiple imputation (Rubin, 1987) to provide the final results.

The J2R sensitivity analysis was implemented using macros developed by the DIA (Drug Information Association) Missing Data Working Group, which were available on page of www.missingdata.org.uk.

To get correct variance for the jump-to-reference imputation method, a pattern mixture model approximation will also be used. Based on the definition, the jump-to-reference imputation will have 0 mean treatment difference between treatment and control for those who dropped out in the treatment arm. Therefore, the overall mean treatment difference for jump-to-reference becomes

$$\theta^{J2R} = (\pi_t \mu_t^d + (1 - \pi_t) \mu_t^p) - \mu_t^p = \pi_t (\mu_t^d - \mu_t^p)$$

where π_t is the proportion of completers in the drug group, t is the last time point, and μ_t^d and μ_t^p are the mean effects for drug and control, respectively. It can be estimated from the primary analysis model as $\hat{\theta}^{J2R} = \hat{\pi}_t (\hat{\mu}_t^d - \hat{\mu}_t^p)$. The variance can be approximated by,

$$\text{var}(\hat{\theta}^{J2R}) = \hat{\pi}_t^2 \text{var}(\hat{\mu}_t^d - \hat{\mu}_t^p) + (\hat{\mu}_t^d - \hat{\mu}_t^p)^2 \hat{\pi}_t (1 - \hat{\pi}_t) / n$$

where n is sample size in the drug treatment arm. The first term can be estimated from the primary analysis model.

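### The sSAP's post-baseline requirement is not lifted for the LCQ jump-to-reference and tipping-point analyses, so read literally it drops participants with no post-baseline LCQ from both

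*Combined protocol and SAP*

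**What the plan says.** Protocol 9.5.1 defines the efficacy population without any post-baseline condition: "The FAS population consists of all randomized participants who have taken at least 1 dose of study intervention". sSAP 3.5.1, repeated in the sSAP 3.1 summary, keeps that definition but adds for change-from-baseline endpoints that "participants need to have baseline and at least one post-baseline measurement for inclusion in the analysis of each specific endpoint". The primary endpoint, LCQ change from baseline at Week 12, is one of these.

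sSAP 3.6.1 bases all efficacy analyses on the FAS and names the LCQ time points: "The LCQ is collected at baseline and after administration of the study intervention at Weeks 6 and 12". It then specifies two sensitivity analyses for missing primary-endpoint data.

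- **Tipping point:** "missing data are first imputed for all visits under the MAR assumption". Step 2 reads "Applying parametric regression to the monotone-missing datasets, impute all the missing values". Step 3 shifts the active arm only, while the closing text says that "all missing data across the arms are assumed to have a worse response by a constant amount of c", and the sSAP change log describes a two-dimensional version.
- **J2R:** "missing data in the treatment groups are imputed under a MNAR assumption using the control group profile for time points after withdrawal". A closed-form approximation follows, in which pi_t "is the proportion of completers in the drug group" and n is the drug-arm sample size.

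Neither description states which participants enter, and neither lifts the rule in 3.5.1. That section does end by sending the reader to Section 3.6 for the handling of missing data.

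**The concern.** For the mixed model the added rule is neutral, because a participant with no post-baseline LCQ contributes no response. For an imputation analysis it is not. Participants whose outcome is wholly unobserved are the ones on whom the missing-data assumption bears most. If they are removed before imputation, less is imputed, so the J2R penalty shrinks and the tipping shift grows with no change in the observed data. The sSAP itself treats a larger tipping shift as a sign of robustness.

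Two programmers could each follow the sSAP and report different J2R estimates and tipping shifts. At stake is how these two analyses are read, not the primary test.

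**Working it through.** **Inputs from the documents** (sSAP 3.9): 207 per arm, 15% dropout at Week 12, difference 1.1, SD 3.5, final one-sided alpha 0.024.

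**The plan's own figures.** 414 × 0.85 = 351.9, the stated 352 evaluable. With 176 per arm, power is 83.4%, consistent with at least 80%.

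**Assumption.** Let f be the share of dropouts with no post-baseline LCQ. The documents do not give it.
- A constant loss rate that reaches 15% at Day 84 puts 1 − 0.85^(42/84) = 7.8% before Day 42. That is 0.078/0.15 = 0.52 of dropouts (0.47 to 0.57 over the ±4-day visit window).
- If a share q of these early leavers gives a Discontinuation-visit LCQ that counts, f = 0.52 × (1 − q): 0.26 at q = 0.5 and 0 at q = 1.
- I therefore show f = 0.25, and f = 0.5 as the approximate upper end under this loss pattern.

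**Set used.** Under exclusion, n = 207(1 − 0.15f) per arm, and the share of the set observed at Week 12 is pi = 0.85/(1 − 0.15f). The standard error of the primary difference is SE = 3.5 × √(2/(207 × 0.85)) = 0.373, held fixed throughout.

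**J2R estimate** = 1.1 × pi. **Active-only tipping shift** (two-sided p crossing 0.05): c = (1.1 − 1.96 × 0.373)/(1 − pi) = 0.369/(1 − pi).

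| Set | Excluded per arm | pi | J2R | Shift c |
|---|---|---|---|---|
| Protocol FAS | 0 | 0.850 | 0.935 | 2.46 |
| Literal rule, f = 0.25 | 7.8 | 0.883 | 0.971 | 3.15 |
| Literal rule, f = 0.5 | 15.5 | 0.919 | 1.011 | 4.55 |

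**Does J2R move?** The multiple-imputation version (steps 1 to 3) does not use pi_t, so it follows the set that is imputed. A simulation with an assumed Week 6 to 12 correlation of 0.6 and an assumed Week 6 effect of 0.9 agrees with the table: 0.93 with these participants kept, and 0.96 (f = 0.26) or 1.01 (f = 0.52) without them, Monte Carlo error about 0.01. The closed-form version moves only if pi_t is computed on the reduced set. On the whole arm it stays at 0.935.

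**Does significance move?** With the sSAP variance, pi² × SE² + 1.1² × pi(1 − pi)/n, z is 0.935/0.318 = 2.94 on the FAS and 1.011/0.344 = 2.94 at f = 0.5. With Rubin's rule in the same simulation, z is about 2.5 kept and 2.6 to 2.7 excluded. J2R is significant in every case.

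**Shift in both arms.** With equal dropout a common shift cancels and never tips on either reading, and the values of c above then apply to the gap between the two arms' shifts. A common shift tips only if dropout differs. With an assumed 20% active and 10% placebo, SE is 0.374, and the gap between the arms' missing shares is 0.100 on the FAS, 0.081 at f = 0.25 and 0.058 at f = 0.5. The tipping shift is then 3.67, 4.54 and 6.28.

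**The case against.** The strongest reply is that the text already points to full inclusion. Section 3.5.1 hands missing data to Section 3.6, and there the wording is broad: "missing data are first imputed for all visits under the MAR assumption", "Applying parametric regression to the monotone-missing datasets, impute all the missing values", and a completer proportion worded for the whole drug group. A specific section would normally prevail over a general sentence. This stands as evidence of likely intent. It does not settle the matter, because those phrases say which values are imputed and not which participants enter. All missing values can be imputed within a set that has already been restricted.

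The second reply is that few participants should be affected. The rule asks for any post-baseline value. The Schedule of Activities has an LCQ at the Discontinuation Visit, protocol 8.10.3 asks for that visit as soon as possible, and protocol 8.1.9 extends its activities to study withdrawals. This stands, and it is why f near 0.5 is an upper end rather than a planning value. Some early leavers may still give no such LCQ.

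A reader might infer that exclusion makes every version of both analyses look milder. The documents do not support that: the J2R formula is unchanged with a whole-arm pi_t, and a common shift with equal dropout never tips. A reader might also infer that the trial's conclusion is at risk, or that the sponsor meant to exclude these participants. Neither follows: no hypothesis or alpha depends on these analyses, and the imputation wording leans the other way.

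**Conclusion.** The gap in the text is real and its reach is limited. The sSAP states an inclusion rule that, followed as written, removes participants with no LCQ after baseline from the two analyses meant to test the missing-data assumption, and nothing in 3.6.1 lifts it. Under exclusion, the multiple-imputation J2R estimate and the active-only tipping shift look more robust than on the protocol FAS, by the amounts in the table.

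The size rests on the planning values, on equal 15% dropout, and on f, which is unknown and could be near 0. The upper end of about 0.5 assumes a constant loss rate and no Discontinuation-visit LCQs. Participants who leave after a Week 6 LCQ stay in on either reading. The wording should be settled before unblinding, but the primary analysis does not depend on it.

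**What to change.** In sSAP 3.5.1 and 3.6.1:
1. Limit the post-baseline requirement to the mixed-model analysis.
2. State that the J2R and tipping-point analyses include all FAS participants with a baseline LCQ, with Weeks 6 and 12 imputed where missing.
3. Compute pi_t and n in the J2R formula on that same set.

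The cost is a few sentences before unblinding and no new data, with up to about 16 more participants per arm to impute. The downside is slightly less favourable sensitivity results than under the literal rule. If full inclusion was always intended, the edit only confirms it.
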